# 8.4. Pharmacokinetics

At the visits and times specified in the SoA, blood samples will be collected for all participants, regardless of whether participants transition to prefilled pen during the study. Only samples from participants assigned to treatment with LY3209590 will be analyzed for drug concentration.

Instructions for the collection and handling of blood samples will be provided by the sponsor.

The actual date and time (24-hour clock time) of each sampling will be recorded.

# **Bioanalytical**

Samples will be analyzed at a laboratory designated by the sponsor and stored at a facility designated by the sponsor. Concentrations of LY3209590 will be assayed using a validated bioanalytical method.

Sample retention is described in Section 10.1.12.

# 8.5. Pharmacodynamics

Pharmacodynamic parameters are described as part of the efficacy assessments in Section 8.1.

### 8.6. Genetics

Genetics are not evaluated in this study.

### 8.7. Biomarkers

Serum and plasma samples will be used for exploratory biomarker research, where local regulations allow. See Clinical Laboratory Tests in Section 10.2, and the SoA for sample collection information.

Samples will be used for research on the drug target, disease process, variable response to LY3209590 pathways associated with T2D, mechanisms of action of LY3209590 or research methods, or in validating diagnostic tools or assay(s) related to T2D.

Samples may be used for research to develop methods, assays, prognostics, and/or companion diagnostics related to the intervention target, disease state, pathways associated with disease, and/or the mechanism of action of the study intervention.

Sample retention is described in Section 10.1.12.

# 8.8. Immunogenicity Assessments

At the visits and times specified in the SoA, venous blood samples from all study participants will be collected to determine antibody production against LY3209590. Antibodies may be further characterized for cross-reactive binding to endogenous insulin.

To interpret the results of immunogenicity, a corresponding venous blood sample will be collected at the same visits to determine the concentrations of LY3209590 (PK sample). At Visit 3, the sample for immunogenicity should be taken before dosing and the PK sample for LY3209590 after dosing.

Instructions for the collection and handling of blood samples will be provided by the sponsor.

TE ADA is defined in Section 9.3.6.2.

Immunogenicity will be assessed by a validated assay designed to detect and characterize ADA in the presence of LY3209590 at a laboratory approved by the sponsor.

Sample retention is described in Section 10.1.12.

# 8.9. Health Economics

Health economics parameters are not evaluated in this study.

# 9. Statistical Considerations

The first version of the SAP will be finalized prior to the first participant visit, and it will include a more technical and detailed description of the statistical analyses described in this section. This section is a summary of the planned statistical analyses of the most important endpoints, including primary and key secondary endpoints.

# 9.1. Statistical Hypotheses

# **Primary Hypothesis**

The primary objective of this study is to test the hypothesis that LY3209590 is not inferior to insulin glargine on glycemic control as measured by change in HbA1c from baseline to Week 52 (Visit 33) in participants with T2D who are starting basal insulin for the first time.

The null hypothesis ( $H_0$ ) is the difference between LY3209590 versus insulin glargine in the change from baseline to Week 52 (Visit 33) in HbA1c is greater than the NIM.

The NIMs of 0.4% and 0.3% will both be tested to meet regulatory requirements. The 2-sided 95% CI will be used for testing the noninferiority.

# **Secondary Hypothesis**

The key secondary (gated) objective is to test the hypothesis that LY3209590 is superior to insulin glargine for change from baseline to Week 52 (Visit 33) in HbA1c.

 $H_0$ : the difference (LY3209590-insulin glargine)  $\geq$ 0.0.

A gatekeeper approach (Westfall and Krishen 2001) will be used to control for type I error for the primary and gated secondary objective.

# 9.2. Analyses Sets

This table defines the populations for the purpose of analysis.

Analysis Populations or Datasets	Description		
Entered Population	All participants who sign the informed consent form.		
Randomized Population	All randomized participants. Participants will be analyzed according to		
	the treatment they were assigned.		
Modified Intent-to-Treat (mITT)	All randomized participants who took at least 1 dose of study treatment.		
Population	Participants will be analyzed according to the treatment they were		
	assigned.		
Efficacy Analysis Set 1 (EAS1) for	The data will include		
treatment regimen estimand	mITT Population excluding participants discontinuing the		
	study treatment due to inadvertent enrollment, and		
	all measurements regardless of the use of study treatment or		
	rescue medications.		
Efficacy Analysis Set 2 (EAS2) for	The data will include		
efficacy estimand	mITT Population excluding participants discontinuing the		
	study treatment due to inadvertent enrollment, and		
	measurements up to the discontinuation of study treatment or		
	the initiation of rescue medication.		

Safety Analysis Set (SS)	The data will include
	mITT Population, and
	all measurements regardless of the use of study treatment or
	rescue medications.

# 9.3. Statistical Analyses

### 9.3.1. General Considerations

Statistical analysis of this study will be the responsibility of Lilly or its designees.

Any change to the data analysis methods described in the protocol will require an amendment ONLY if it changes a principal feature of the protocol. Any other changes to the data analysis methods described in the protocol, and the justification for making the change, will be described in the SAP or the final clinical study report. Additional exploratory analyses of data will be conducted as deemed appropriate.

Unless otherwise stated, the efficacy analyses will be conducted on either EAS1 or EAS2, and the safety analyses will be conducted on the SS. All tests of treatment effects will be conducted at a 2-sided alpha level of 0.05 and 2-sided 95% CIs will be calculated.

Unless otherwise stated, the other secondary and tertiary efficacy measures will be analyzed using the data up to the discontinuation of study treatment (EAS2), defined by the date of last study dose +10 days or the initiation of rescue medication, whichever is earlier.

Handling of missing, unused, and spurious data are addressed prospectively in the overall statistical methods described in the protocol and in the SAP, where appropriate. Adjustments to the planned analyses are described in the final clinical study report.

# 9.3.2. Primary Endpoint or Estimand Analysis

The primary objective is to compare the HbA1c change from baseline to Week 52 (Visit 33) between LY3209590 and insulin glargine and will be based on either of these 2 estimands:

treatment regimen estimand for registration in the United States, and efficacy estimand for registration in other countries.

The 2-sided 95% CI of the LS mean for individual treatment groups and treatment LS mean difference for the HbA1c change from baseline to Week 52 (Visit 33) will be estimated.

For both estimands, LY3209590 will be declared noninferior to insulin glargine if the upper limit of the 2-sided 95% CI for the LS mean difference in the HbA1c change from baseline is below NIM (+0.4% or +0.3% for different regulatory requirements).

The HbA1c is reported in unit of % and will be converted to the unit of mmol/mol using this formula:

HbA1c in mmol/mol = 10.93 \* HbA1c in % - 23.5 (NGSP, 2010).

# Treatment regimen estimand

The treatment regimen estimand will be based on the HbA1c data at baseline and Week 52 (Visit 33) for the EAS1, regardless of the use of study intervention or rescue medications.

# Missing measures

Missing measures at the primary endpoint will be imputed using multiple imputation by the retrieved dropout approach. The retrieved dropout participants are those who discontinue study intervention prior to Week 52 (Visit 33) but have non-missing measures at Week 52 (Visit 33).

If there are only a limited number of retrieved participants that leads to a failure in performing the multiple imputation analysis, such as the model cannot converge, or the number of retrieved dropout participants is small, the missing HbA1c at Week 52 (Visit 33) will be imputed by return-to-baseline multiple imputations.

### Analysis model

After the imputation, the observed and imputed data will be analyzed by the ANCOVA. The model will include treatment (LY3209590 and insulin glargine), strata (country, GLP-1 RA treatment at randomization), and baseline value of the dependent variable. The statistical inference will be based on the multiple imputation framework by Rubin (1987).

### **Efficacy estimand**

The efficacy estimand is the treatment difference in the change of HbA1c from baseline to Week 52 (Visit 33) if all participants adhere to the treatment without intercurrent events.

The HbA1c collected at all planned postbaseline visits from the EAS2 will be used in the analysis.

# Missing measures

There may be missing values due to the early discontinuation of study treatment or use of rescue medication.

# Analysis model

The MMRM model will be used, and the missing values will be handled in the MMRM analysis under the assumption of missing at random. The MMRM model will include treatment (LY3209590 and insulin glargine), strata (country, GLP-1 RA treatment at randomization), visit and treatment-by-visit interaction as fixed effects, and baseline of the dependent variable as a covariate. The Kenward-Roger approximation will be used to estimate denominator degrees of freedom for the MMRM models.

An unstructured covariance structure will be used to model the within-participant errors. If this structure fails to converge, the following covariance structures will be used in order until one converges:

- 1. Toeplitz with heterogeneity
- 2. autoregressive with heterogeneity
- 3. compound symmetry with heterogeneous variances
- 4. Toeplitz
- 5. autoregressive
- 6. compound symmetry without heterogeneous variances.

Change in LY3209590 administration device, from autoinjector to prefilled pen, will not be considered as an intercurrent event. Thus, the 2 estimands described above will include all participants who received LY3209590 study treatment irrespective of the administration device.

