## 4.2. Scientific Rationale for Study Design

#### **Primary endpoint**

The primary efficacy measurement is HbA1c, a widely used measure of glycemic control that reflects a cumulative history of glucose levels in the preceding 2 to 3 months.

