## 6.3. Measures to Minimize Bias: Randomization and Blinding

#### Randomization and stratification

All participants will be centrally assigned to randomized study intervention using an IWRS. Before the study is initiated, the login information and directions for the IWRS will be provided to each site.

Participants will be randomly assigned in an 1:1 ratio to LY3209590:insulin glargine.

Participants will be stratified based on

- country
- HbA1c stratum at Visit 1 (<8% and  $\ge8\%$ ), and
- GLP-1 RA use at randomization, regardless of oral or injectable administration, (Yes/No).

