# 9.5. Sample Size Determination

Approximately 670 participants will be randomly assigned to LY3209590 and insulin glargine in a 1:1 ratio.

With the assumption of 15% dropout at Week 52 (Visit 33), approximately 284 participants on LY3209590 and 284 participants on insulin glargine will complete 52 weeks of treatment.

The number of completers will provide at least 99% statistical power to show noninferiority between LY3209590 and insulin glargine using the upper limit of a 2-sided 95% CI and these assumptions

- NIM of 0.4%
- no true difference between treatment groups, and
- an SD of 1.1%.

This sample size has at least 90% statistical power to show noninferiority between LY3209590 and insulin glargine using a 0.3% NIM at Week 52 (Visit 33).

The number of completers will provide 90% statistical power to show superiority between LY3209590 and insulin glargine for change in HbA1c from baseline to Week 52 (Visit 33), assuming an SD of 1.1% and true mean difference of -0.3%, and alpha of 0.05.

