#### 4.3.2. Main Analytical Approach

The primary objective is to test the hypothesis that LY3209590 is noninferior to insulin glargine on glycemic control in the targeted study population. The noninferiority test will be based on

either of the 2 estimands: *treatment regimen estimand* for the US FDA submission and *efficacy estimand* for registrations in other countries. The full significance level of 0.05 will be used for each estimand.

This table provides the details of treatment regimen estimand and efficacy estimand.

	Treatment Regimen Estimand	Efficacy Estimand
Analysis Population	All participants in EAS1 with non-missing baseline measure	All participants in EAS2 with non- missing baseline measure and at least one non-missing postbaseline scheduled measure
Analysis Data	All non-missing observations at baseline and Week 52 (Visit 33) regardless of the use of study intervention or rescue medications.	All non-missing observations at baseline and all scheduled postbaseline timepoints during treatment period (that is, Weeks 2, 4, 8, 12, 16, 26, 36, and 52) prior to the date of last study dose + 10 days for LY3209590 (+1 day for Glargine), or the initiation of rescue medication, whichever is earlier for participants with intercurrent events.
Missing Data	There may be missing values at Week 52 (Visit 33) due to early study discontinuation. The missing values will be imputed using multiple imputation by the retrieved dropout approach. The retrieved dropout participants are those who discontinue study intervention prior to Week 52 but have non-missing measures at Week 52 in the same treatment arm. If there are only a limited number of retrieved participants that leads to a failure in performing the multiple imputation analysis, such as the model cannot converge, or the number of retrieved dropout participants is small (i.e., at least 1 arm has < 8 participants who discontinued study treatment early and have endpoint visit measurements), the missing HbA1c at Week 52 will be imputed by return-to-baseline multiple imputation approach (Qu and Dai, 2022).	There may be missing values due to the early discontinuation of study intervention or use of rescue medication. The MMRM model will be used, and the missing values will be handled in the MMRM analysis under the assumption of missing at random.

	Treatment Regimen Estimand	Efficacy Estimand
Analysis Model	After the imputation, the observed	The MMRM model will include

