	and imputed data will be analyzed by	treatment, strata (country and GLP-1 RA
	the ANCOVA model using	treatment at randomization), visit and
	treatment, strata (country and GLP-1	treatment-by-visit interaction as fixed
	RA treatment at randomization), and	effects, and baseline of the dependent
	baseline value of the dependent	variable as a covariate. The Kenward-
	variable as independent variables.	Roger approximation will be used to
	The statistical inference will be based	estimate denominator degrees of freedom
	on the multiple imputation	for the MMRM models. An unstructured
	framework by Rubin (1987).	covariance structure will be used to
		model the within-participant errors. If this
		structure fails to converge, the following
		covariance structures will be used in
		order until one converges:
		1. Toeplitz with heterogeneity
		2. autoregressive with
		heterogeneity
		3. compound symmetry with
		heterogeneous variances
		4. Toeplitz
		5. Autoregressive
		6. compound symmetry without
		heterogeneous variances.

Abbreviations: ANCOVA = analysis of covariance; EAS1 = efficacy analysis set 1; EAS2 = efficacy analysis set 2; GLP-1 RA = glucagon-like peptide-1 receptor agonist; HbA1c = hemoglobin A1c; MMRM = mixed model repeated measurement.

The 2-sided 95% CI of the LS mean difference (LY3209590 – insulin glargine) in the HbA1c change from baseline to Week 52 (Visit 33) will be estimated. For both estimands, LY3209590 will be declared noninferior to insulin glargine if the upper limit of the 2-side 95% CI for the LS mean difference in the HbA1c (measured in %) change from baseline is below NIM of +0.4%. In addition, the 95% CI for the LS mean difference will be compared to an alternative NIM of +0.3%.

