#### 4.3.3.3. Other Sensitivity Analysis

The following sensitivity analyses will be performed using the same MMRM model as for the efficacy estimand described in Section 4.3.2 based on the EAS2 data.

- Sensitivity analysis will be conducted excluding the data after the change to LY3209590 with a prefilled pen to compare the HbA1c change from baseline to Week 52 (Visit 33) between LY3209590 with the autoinjector and insulin glargine.
- To balance the exposure time for LY3209590 with autoinjector and insulin glargine, sensitivity analysis will be conducted to compare the HbA1c change from baseline to Week 52 (Visit 33) for participants receiving LY3209590 with autoinjector for the whole treatment period and participants receiving insulin glargine.

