## 4.7.2.1. Subgroup Analyses in HbA1c

Subgroup analyses in HbA1c and change in HbA1c from baseline to Week 52 will be conducted with subgroups defined as:

- Age (<65 years and  $\ge65$  years)
- Baseline HbA1c stratum (<8.0% and  $\ge8.0\%$ )
- Ethnicity
- Gender
- Race (White, American Indian or Alaska Native, Asian, and Black or African American)
   Native Hawaiian or Other Pacific Islander, and Multiracial are not included in the subgroup analysis because the number of subjects is too small.
- Region (US and non-US)
- Region (North America and South America)
- GLP-1 RA use at randomization
- Estimated Glomerular Filtration Rate (eGFR) at baseline ( $<60, 60 <90, and <math>\ge 90$  mL/min/1.73 m^2)
- Duration of diabetes (< median and  $\ge$  median)
- Insulin Dose (>400 U at anytime and <= 400 U at anytime), where
  - o ">400 U at anytime" group includes participants receiving insulin glargine with weekly dose >400 U at anytime up to week 52 (Visit 33) or participants who switch to prefilled pen for LY3209590, and
  - "<= 400 U at anytime" group includes participants receiving insulin glargine with weekly dose <=400 U at anytime up to Week 52 (Visit 33) or participants receiving LY3209590 with auto injector for the whole treatment period.

Analyses for HbA1c and its change will be performed within each subgroup using the same MMRM model for efficacy estimand described for the primary analysis in Section 4.3.2. In addition, the interaction effects will be assessed using the model including the same fixed effects and covariate given for the primary analysis model plus factors of subgroup, 2-way interaction of

subgroup and treatment, 2-way interaction of subgroup and visit, and 3-way interaction of treatment, visit and the subgroup.

Another subgroup analysis for HbA1c will be conducted for treatment regimen estimand. The ANCOVA analysis for HbA1c for the treatment regimen estimand as described in Section 4.3.2. will be performed within each subgroup. The statistical inference will be based on the multiple imputation framework by Rubin (1987). The p-value for treatment by subgroup interaction will be calculated using a chi-square test based on estimated treatment differences within each subgroup. (See details in Appendix 11 [Section 6.11]).

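### The HbA1c MMRM for the efficacy estimand uses one baseline slope for Weeks 2 to 52, so the Week 52 comparison loses part, often more than half, of the precision that baseline adjustment could give

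*Protocol*

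**What the plan says.** Protocol 9.3.2 (efficacy estimand, analysis model) lists the terms of the HbA1c MMRM: treatment, country, GLP-1 RA use at randomization, then "visit and treatment-by-visit interaction as fixed effects, and baseline of the dependent variable as a covariate". SAP 4.3.2 repeats the list, and treatment-by-visit is the only interaction in either document. The first-choice covariance is unstructured. The data entering the model are the "timepoints during treatment period (that is, Weeks 2, 4, 8, 12, 16, 26, 36, and 52", eight post-baseline visits in all.

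The model serves registration outside the United States. It also carries the gated superiority test for this estimand, and SAP 4.3.3.3 reuses it: "The following sensitivity analyses will be performed using the same MMRM model as for the efficacy estimand". The treatment regimen ANCOVA uses Week 52 only, so it has its own Week 52 slope and is not affected.

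Protocol 6.3 stratifies randomization on "HbA1c stratum at Visit 1" (below 8% versus 8% or more). That stratum is not in the HbA1c MMRM, so continuous baseline HbA1c is the model's only adjustment for starting glycemia.

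**The concern.** Protocol 4.2 says that HbA1c "reflects a cumulative history of glucose levels in the preceding 2 to 3 months". At Weeks 2 and 4 a participant's HbA1c is therefore still largely the baseline value, and its change depends little on baseline. By Week 52 participants who start higher can be expected to have fallen further, so the slope of change on baseline should be clearly negative.

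A model with one slope must compromise. Under an unstructured covariance the compromise is a precision-weighted average. The early visits, where change varies least, get the most weight, so the fitted slope sits near zero. At Week 52 the analysis then behaves more like an unadjusted comparison of change scores than a baseline-adjusted one.

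At stake is the width of the Week 52 confidence interval. The sample size section claims about 90% power for noninferiority at the 0.3% margin ("This sample size has at least 90% statistical power to show noninferiority") and for superiority at a true difference of -0.3%. Those two tests have the least power to spare.

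**Working it through.** **1. The plan's own figures.** Inputs from Protocol 9.5: SD 1.1%, 284 completers per arm, true difference 0, two-sided 95% CI.

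SE = 1.1 × √(2/284) = 0.0923. Power = Φ(margin/SE − 1.96).

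- Margin 0.3%: Φ(3.25 − 1.96) = 90.1% (noncentral t: 90.05%).
- Margin 0.4%: Φ(4.33 − 1.96) = 99.1%.

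Both reproduce, with no credit taken for baseline adjustment.

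**2. Formulas for the loss.** Let b be the vector of true visit slopes of change on baseline, S the covariance of the visits given baseline, v the baseline variance, and s² the Week 52 variance given baseline.

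- Fitted common slope: β = (1′S⁻¹b)/(1′S⁻¹1). Including the misfit (b − β1)(b − β1)′v in the weighting covariance and iterating leads to the same β.
- Week 52 residual variance under the common slope: s² + (b₅₂ − β)²v.
- Variance ratio, common slope to visit-specific slopes: 1 + (b₅₂ − β)²v/s².
- Share of the adjustment gain lost, relative to unadjusted change: (b₅₂ − β)²/b₅₂².

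**3. Two worked cases.** All inputs here are assumptions. The SD of Week 52 change is close to 1.1% in both, and power is at the 0.3% margin with 284 per arm.

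| | Moderate case | Strong-baseline case |
|---|---|---|
| Baseline SD (v) | 0.70 (0.49) | 0.85 (0.7225) |
| b₅₂, β | −0.60, −0.205 | −0.652, −0.123 |
| s² | 1.21 − 0.36 × 0.49 = 1.034 | 0.934 |
| (b₅₂ − β)²v | 0.156 × 0.49 = 0.076 | 0.280 × 0.7225 = 0.202 |
| Variance ratio | 1.07 | 1.22 |
| CI widening | √1.074: 3.6% | √1.216: 10.3% |
| Share of gain lost | 0.156/0.36 = 43% | 0.280/0.425 = 66% |
| Power, common slope | 92.4% | 91.8% |
| Power, visit-specific | 94.0% | 95.9% |

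**4. Simulation of the moderate case.** 150 replicates, 670 participants, randomization stratified on screening HbA1c, 14% dropout missing at random, unstructured fit. The mean model SE was 0.0861 with the common slope and 0.0832 with visit-specific slopes; (0.0861/0.0832)² = 1.07, as the formula gives. Mean estimates were 0.001 and 0.002 against a true value of 0. Coverage was 96.7% and 96.0%.

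**5. Range over assumptions.** The first two rows assume total SD 1.1%, baseline SD 0.60 to 0.85 (a uniform spread over 7.0% to 10.0% would give 3/√12 = 0.87), a Week 52 slope of −0.4 to −0.7 and a response time constant of 5 to 10 weeks. The last two rows use baseline SD 0.7 to 1.0.

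| Assumed structure | Settings | Median variance ratio | More than half of gain lost |
|---|---|---|---|
| Move to an individual plateau | 648 | 1.08 (5th–95th percentile 1.03–1.25) | 73% of settings |
| Autoregressive residuals, larger early variance | 648 | 1.07 (1.02–1.23) | 54% |
| Exponential-decay correlation | 324 | 1.14–1.18 over these two rows, where SD of change is 1.0–1.2 | 57% |
| HbA1c-memory model | 1944 | as above | 59% |

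In the first row the median share lost is 60% (23% to 85%) and the CI is 4% wider (1% to 12%). In completers, 284 × (1 − 1/1.08) ≈ 21 per arm. Median power at the 0.3% margin is 91.3% as planned and 93.5% with visit-specific slopes, with a median gain of 1.9 points (0.3 to 5.8). In the second row planned power reaches 90% in 96.5% of settings (minimum 89.6%).

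Under equal-variance compound symmetry the ratio is only 1.00 to 1.04, with 3% to 10% of the gain lost. If the baseline relation does not change over visits, the loss is zero.

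**The case against.** The case for leaving the model alone is substantial, and much of it stands.

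- **No design target is missed.** The stated power takes no credit for baseline adjustment, and power at the 0.4% margin is about 99% either way. This stands: what is lost is surplus precision.
- **The percentages count chosen settings and are not probabilities.** This also stands. A share of the gain sounds larger than the absolute effect, which is a few percent of CI width. The documents also do not say whether 1.1% is a raw or a residual SD; the figures above treat it as the SD of change.
- **Stratifying on Visit 1 HbA1c makes the under-adjusted estimate less variable than its model SE suggests.** This is correct. If stratification halves the variance of the between-arm baseline difference (roughly what was found), the true variance in the moderate case is 1.034 + 0.038 = 1.072. Power is then Φ((0.3 − 1.96 × 0.0884)/0.0869) = 92.8%, not 92.4%, and the benefit of the change falls from 1.6 to 1.2 points. The reported interval stays as wide.
- **SAP 4.7.2.1 does not contradict the primary model.** Its "2-way interaction of subgroup and visit" is a routine lower-order term beneath a three-way interaction and is applied to every subgroup. It is weak evidence that the sponsor expects a visit-varying baseline effect.
- **Adding the HbA1c stratum would not help.** A stratum main effect would also be constant over visits.
- **The SAP is at version 3 and already revised after regulatory feedback.** Changing a primary model for precision alone needs a documented reason. That is a cost, though a small one before unblinding.

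**Conclusion.** The concern holds as a point about efficiency. The text fixes one baseline slope for Weeks 2 to 52, and nothing else in either document supplies a visit-specific baseline term. With the first-choice unstructured covariance, the Week 52 contrast gives up a share of the adjustment gain that depends on assumptions and exceeds one half in most, though not all, of the settings tried.

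In absolute terms the effect is modest: a Week 52 variance typically 7% to 15% larger than necessary, an interval about 4% wider in the main set of settings, and about 2 points of power at the 0.3% margin. The estimate is not materially biased, type I error is not inflated, and the sample size statement is correct. The result depends on the baseline slope steepening over the year, which Protocol 4.2 makes plausible but no figure in the documents establishes. Of the fallback covariance structures only equal-variance compound symmetry was quantified, and there the loss is small.

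The change is worth making because it costs little and benefits the tests with the least power to spare. It is not a condition for a valid analysis.

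**What to change.** Add a baseline-HbA1c-by-visit interaction to the efficacy-estimand MMRM in Protocol 9.3.2 and SAP 4.3.2 before unblinding. The HbA1c models that reuse it would inherit the term: the sensitivity analyses in SAP 4.3.3.3, Week 26 HbA1c in SAP 4.4.2.1 and the subgroup MMRMs in SAP 4.7.2.1. For the subgroups, state explicitly whether the term is kept where a subgroup is small, and in the baseline-HbA1c-stratum interaction model, where it overlaps with stratum-by-visit. The SMBG and insulin-dose models are outside this point.

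The cost is seven extra parameters with about 670 participants, and no new data. SAP 4.9 and SAP 1 now report no changes from the protocol, so each needs an entry with the justification. Under Protocol 9.3.1 the sponsor must also decide whether this alters a principal feature and so requires an amendment. The timing matters: a covariate form chosen after unblinding would carry little weight.
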